9.3. Variables

The variables to be collected are listed in [Table 9-1](#).

9.3.1. Exposure

Data on Truvada for PrEP will be collected. The start and stop dates will be used to estimate person-time of exposure to Truvada. Person-time of exposure will be defined as ([PrEP end date - PrEP initiation date] + 1), regardless of temporary interruptions in exposure (< 30 days) and will be expressed in days (recorded in whole days, eg, 41 days). Exposure starts the first day the medication was prescribed or self-initiated (and assumed to have been taken). An individual may have multiple exposures defined as the re-initiation of PrEP after a period of stoppage that is greater than 30 days. Aggregated person-time may also be expressed in person-years ([number of person days]/365.25). Individuals who are taking PrEP on an intermittent or event-driven basis will have exposure calculated in a similar fashion ([PrEP end date - PrEP initiation date] + 1).

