9. RESEARCH METHODS

9.1. Study Design

This is a prospective, longitudinal, observational, and voluntary participation registry designed to characterize the real-world use of Truvada for PrEP to prevent HIV-1 infections in adults and adolescents in Europe. The individuals who agree to participate in the registry will receive treatment solely based on current clinical practice in the country in which they reside. The use of Truvada for PrEP should be within the conditions of its approved SmPC. However, Gilead will not influence decision making by the participating HCPs or restrict enrollment into the registry to those individuals who are not receiving drug in full compliance with the SmPC (where local regulations allow to do so) as the objective of the registry is to describe the patterns of use and monitoring in real life. Data on intermittent use of Truvada for PrEP will be collected in countries permitting such data collection.

Both male and female adults and adolescents will be recruited for enrollment in the registry. Individuals who started Truvada for PrEP prior to first presenting to the participating HCP or are prescribed Truvada for PrEP will be eligible for enrollment. Baseline will be considered as the start date of Truvada for PrEP. The data for individuals receiving Truvada for PrEP prior to enrollment will be collected retrospectively from the individual's medical record.

Individuals will be followed while on Truvada for PrEP and the frequency of clinic visits will be at the discretion of the prescribers. Individuals will be followed until they are either lost to follow up, discontinued Truvada for PrEP, become infected with HIV, withdraw consent, or registry closure.

Details on Truvada for PrEP use, the healthcare Institution characteristics, and prescriber characteristics will also be collected .

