Recruitment methods within each country will begin by assessing if they have a national policy for PrEP or a similar initiative that would support reimbursement of all HIV-1 PrEP medicinal products or only Truvada or generic equivalents products. HCPs who prescribe products for HIV-1 PrEP will be contacted to determine if they prescribe Truvada for PrEP and if so they will be invited to participate in the registry. Additionally, a review of planned, ongoing, or completed clinical studies or demonstration projects which include Truvada for PrEP will be carried out to identify potential individuals who have completed or discontinued participation in the study but continue to take Truvada for PrEP.

A written contract on the implementation of this registry shall be concluded between sponsor and clinical site. Personnel from the sponsor company or the contract research organization (CRO) will describe the registry to HCPs at each site and provide training on the registry design and data collection to ensure, as much as possible, quality and consistency of data collected. HCPs will only be compensated for their time and efforts on the registry based on current fair market value at the time of contract finalization.

9.2.1. Inclusion Criteria:

- HIV-1 negative adults and adolescents who are deemed to be at high risk for acquiring HIV-1
- HIV-1 negative adults and adolescents who provided consent / assent and, depending on local country regulations, parental or legal guardian permission to participate in the registry
- HIV-1 negative adults and adolescents who are receiving Truvada for HIV PrEP, either as a daily or intermittent regimen, and that are clinically monitored

9.2.2. Exclusion Criteria:

- Individuals currently participating in a clinical study of HIV PrEP

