9.5. Study Size

The purpose of the registry is to provide insight into the patterns of Truvada for PrEP usage and how clinicians are monitoring individuals on Truvada for PrEP. The registry is not designed or powered to compare rates of seroconversion or adherence with studies or demonstration projects.

Enrollment will be open to both adults and adolescents, and enrolled individuals will be followed while Truvada for PrEP is continued. Target is to enroll and follow enough adults to provide at least 400 person-years of follow-up data and enough adolescents to provide at least 25 person-years of follow-up data.

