9.7. Data Analysis

Descriptive data analysis will be used to summarize the available data. There are no statistical hypotheses to evaluate. Categorical variables will be reported by proportions and continuous variables will be reported by mean, standard deviation, minimum, median, and maximum. Prescriber characteristics will be summarized. Demographics and clinical characteristics of individuals on Truvada for PrEP will be analyzed. The products prescribed and available prescription details, the frequency of monitoring, and any relevant data on adherence monitoring will be summarized. Seroconversion cases and results of resistance testing will be summarized. Reports of treatment-related renal and bone adverse drug reactions (SADRs and ADRs) will be summarized. Females participants in the registry who are pregnant will also be analyzed.

Data will be presented overall, and by age group (adolescents and young adults) and risk factors for HIV transmission.

Rates of adherence and new HIV diagnoses (i.e., seroconversion) will be calculated with 95% confidence intervals. Results will be presented overall and by subgroups including adults and adolescents, gender, and country.

Comprehensive information relating to the analysis of this registry will be provided in the statistical analysis plan.

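### Person-time runs from Truvada start, but only HIV-negative current users can enrol: used as the denominator of the seroconversion rate, as the text implies, it biases that rate low

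*Protocol*

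**What the plan says.** Protocol section 9.1 opens the registry to people already on the drug: "Individuals who started Truvada for PrEP prior to first presenting to the participating HCP or are prescribed Truvada for PrEP will be eligible for enrollment". For them, "The data for individuals receiving Truvada for PrEP prior to enrollment will be collected retrospectively from the individual's medical record", and for everyone "Baseline will be considered as the start date of Truvada for PrEP". Section 9.2 adds that former participants in studies and demonstration projects who are still on Truvada will be sought, so prior users are a planned part of the cohort.

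Section 9.3.1 defines exposure time: "Person-time of exposure will be defined as ([PrEP end date - PrEP initiation date] + 1"), summed to person-years. The clock is explicit: "Exposure starts the first day the medication was prescribed or self-initiated (and assumed to have been taken"). The enrolment date plays no part.

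The third inclusion criterion in section 9.2.1 reads "HIV-1 negative adults and adolescents who are receiving Truvada for HIV PrEP, either as a daily or intermittent regimen, and that are clinically monitored". Section 9.1 ends follow-up at HIV infection.

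Section 9.7 promises: "Rates of adherence and new HIV diagnoses (i.e., seroconversion) will be calculated with 95% confidence intervals". It names no denominator. Section 9.5 sets the adult target as "enough adults to provide at least 400 person-years of follow-up data", with 25 person-years for adolescents. Section 11.1.1 starts safety collection at consent.

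**The concern.** A person who started Truvada, acquired HIV and was diagnosed before reaching a participating clinic can never enter the registry. A person who started on the same day and stayed negative can enter, and brings all of the earlier time along. That earlier time adds to the denominator and cannot add to the numerator. This is immortal time, created by left truncation that the person-time definition ignores.

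The seroconversion rate is the one incidence estimate that the protocol promises with a confidence interval, and it serves objective 4. The error can only lower it, which is the direction that favours the product. The interval is also based on more person-time than was at risk of an observable event.

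**Working it through.** **Which denominator.** Section 9.3.1 holds the only person-time definition. The reference rates in section 7.1 are per 100 person-years: 0.4 in the adult demonstration project and 6.4 in the adolescent trial. The checklist in Annex 1 says that a measure of occurrence is specified and points to section 9.7. Together these make section 9.3.1 time the likely denominator, though no sentence says so.

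**Nothing to reproduce.** The 400 and 25 person-years come without a derivation, a precision target or a number of participants.

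**Effect on the rate.** Let T be the counted person-years, f the share of T before enrolment, and λ the true rate, taken as constant. Events can be recorded only in T(1 − f), so:
- expected events = λ × T × (1 − f)
- expected reported rate = λ × T × (1 − f) / T = λ × (1 − f)

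**Effect on the upper limit.** With zero events the exact Poisson two-sided 95% upper limit is −ln(0.025) / person-years = 3.689 / person-years. The reported limit uses T; the correct one uses T(1 − f).

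The protocol does not give f, so it is shown over a range.

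Adults, T = 400, λ = 0.4 per 100 person-years:

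| f | person-years at risk | expected events | reported rate per 100 | correct upper limit per 100, zero events | probability of zero events |
|---|---|---|---|---|---|
| 0 | 400 | 1.6 | 0.40 | 3.689/400 = 0.92 | 20% |
| 25% | 300 | 1.2 | 0.30 | 3.689/300 = 1.23 | 30% |
| 50% | 200 | 0.8 | 0.20 | 3.689/200 = 1.84 | 45% |

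In every row the limit reported under section 9.3.1 would be 0.92.

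Adolescents, T = 25, λ = 6.4 per 100: expected events are again 1.6 at f = 0. The reported rate is 6.4, 4.8 and 3.2 at f = 0, 25% and 50%. With zero events the reported upper limit is 3.689/25 = 14.8 per 100; at f = 50% the correct one is 3.689/12.5 = 29.5.

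**What prior use gives such values of f.** Assume uniform enrolment over 3 years, 6 further months of data collection and no discontinuation. Mean prospective time is then 1.5 + 0.5 = 2.0 years. If every participant brought P years of prior use, f = P / (P + 2.0): 20%, 33% and 50% for P = 0.5, 1 and 2. New users in the mix lower f; early discontinuation after enrolment raises it. If all enrol at initiation, f = 0 and there is no bias.

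**Safety.** Section 11.1.1 collects safety events from consent, and section 11.3.1 treats conditions that began before consent as pre-existing. Any safety rate per section 9.3.1 person-year would shrink by the same factor, 1 − f.

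**The case against.** **The denominator is inferred.** Section 9.3.1 describes exposure, which suits a description of drug use, and does not call it time at risk. Section 9.7 puts adherence and seroconversion in one sentence about rates, and adherence is not naturally a person-time rate. It also leaves detail to the statistical analysis plan, which is not at hand and might set a different start of risk time. This stands, so the conclusion is conditional. But the protocol has already fixed baseline and person-time, and an analysis plan that follows it would inherit the bias.

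**The person-year target.** A reader might infer that 400 person-years could be declared reached from retrospective time alone, with no follow-up. The documents do not support that. Section 9.5 speaks of both enrolling and following people and of follow-up data, and section 9.1 calls the registry prospective; time after enrolment is the natural meaning. What remains is an ambiguity: baseline is Truvada start, and section 9.5 does not say whether retrospective time counts.

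**A ceiling on prior use.** A reader might take the 2016 approval of the PrEP indication as setting the longest possible prior use. It does not: enrolment is planned to Q4 2023, and self-initiators and former study participants are eligible. The documents give no worst case.

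**Importance.** The registry is descriptive, tests no hypothesis and is not meant for comparing seroconversion rates. With about 1.6 expected adult events, sampling error is large beside a moderate bias. This lowers the priority but does not remove the point, since a descriptive rate still needs a matching numerator and denominator. Section 9.9 discusses selection through voluntary participation, not this mechanism, and the Annex 1 item that covers time-related bias is marked not applicable.

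**Conclusion.** The point holds in conditional form and should be fixed. The protocol's rules on eligibility, baseline and person-time, taken together, make pre-enrolment time free of recorded seroconversions. If that time is in the denominator, the rate is multiplied by 1 − f. A 25% or 50% share of pre-enrolment time lowers it by a quarter or a half, and the zero-event upper limit for adults reads 0.92 where 1.23 or 1.84 per 100 person-years is right.

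The direction is certain under that reading; the size is not, because the share and length of prior use are assumptions here. The figures also assume a constant true rate, taken from the adult reference in section 7.1. Safety rates are affected only if they are calculated on the same person-time, and the protocol promises summaries of safety events, not rates. For the person-year targets the finding is an unclear definition, not a route to skipping follow-up.

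**What to change.** - **Sections 9.3.1 and 9.7:** define at-risk person-time for the seroconversion rate, and for any safety rate, as starting at the later of Truvada start and consent/enrolment (delayed entry). Name it as the denominator.
- **Section 9.5:** state that only this time counts toward the 400 and 25 person-years.
- **Description of use:** keep the initiation-based definition for this purpose, and report pre-enrolment exposure separately as history of use.

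The cost is mainly wording. Consent forms are dated (section 10.3). Table 9-1 accepts a duration in place of Truvada dates, so the exact start may be missing for some people; for someone already on Truvada the at-risk clock starts at consent, so the rate does not depend on that date. The downside is fewer person-years and a wider interval, and the targets may take longer to reach if retrospective time had been expected to count.

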9.3.2. Outcomes

- Describe how Truvada for PrEP is prescribed or self-initiated, including the dosing pattern (dose and schedule as daily/intermittent)
- Characterize the demographics of individuals who were prescribed or are taking Truvada for PrEP and their HIV risk factors
- Characterize the nature and frequency of individual monitoring after initiating Truvada for PrEP, including any available information on adherence
- Document any cases of new HIV diagnoses and development of any resistance to Truvada and any treatment-related renal or bone adverse reactions
- Summarize the characteristics of healthcare professionals who prescribe Truvada for PrEP

9.3.3. Items of Surveillance

Data from routine care, as available from medical records, will be collected using electronic case report forms (eCRFs). The following elements will be collected at the approximate intervals as noted in [Table 9-1](#).

Table 9-1. Data Items and Timing for Surveillance

Items of Surveillance	On-Treatment Period		Seroconversion
	Baseline Truvada PrEP initiation	Each Follow-Up Visit	At Time of New HIV Infection
Informed consent	X		
Age	X		
Gender at start of PrEP (Male [M], Female [F], Transgender M-F or F-M)	X		
Weight and Height	X	X	
Self-initiated or prescribed Truvada for PrEP usage details (dose and schedule [continuous/daily or intermittent])	X	X	
Truvada for PrEP start and stop dates or duration of PrEP usage	X	X	X
Product name: (Truvada prescribed or self-sourced)	X	X	X
Assessment of adherence with PrEP	X	X	X
Risk factors for HIV-1	X	X	X
Use of recreational drugs during sex	X	X	X
Sexual transmitted infections – (1) oropharyngeal, (2) urethral/cervicovaginal, (3) rectal, and (4) syphilis	X	X	X
HIV-1 test method(s), results, and dates	X	X	X
Prior use of PrEP (prescribed or self-medicated) or PEP	X		
HBV serostatus	X		
HCV serostatus	X		
If female, pregnancy status	X	X	X
eGFR	X	X	
Serum phosphate	X	X	
Safety data (all fatal Events and all serious adverse drug reactions [SADRs], treatment-related renal or bone adverse drug reactions, and pregnancy reports)	X	X	X

Items of Surveillance	On-Treatment Period		Seroconversion
	Baseline Truvada PrEP initiation	Each Follow-Up Visit	At Time of New HIV Infection
Possible factors leading to new HIV infection			X
Genotypic resistance testing			X
Reason for PrEP discontinuation		X	X

Data on participating institutions and prescribers will be collected at the time of enrollment. Institution information will include country, city, and type of institution. Prescriber information will include medical specialty.

9.3.4. Laboratory Tests

Routinely collected laboratory values and date(s) of test(s) will be captured as available. This registry will collect:

- Virologic testing (HIV test methodology and results, hepatitis B serology, hepatitis C serology)
- Renal function (estimated glomerular filtration rate [eGFR]), serum phosphate
- Genotypic resistance testing (testing results)
- Pregnancy testing (testing results)

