Both adults (≥ 18 years of age) and adolescents weighing at least 35 kg (eg, 12 to 17 years of age) receiving Truvada for PrEP will be included as the primary population for this registry. Furthermore, the registry will collect data on HCPs who prescribe Truvada for PrEP.

Inclusion criteria:

- HIV-1 negative adults and adolescents who are deemed to be at high risk for acquiring HIV-1
- HIV-1 negative adults and adolescents who provide consent / assent and, depending on local country regulations, parental or legal guardian permission to participate in the registry
- HIV-1 negative adults and adolescents who are receiving Truvada for HIV PrEP, either as a daily or intermittent regimen, and that are clinically monitored

Exclusion criteria:

- Individuals currently participating in a clinical study of HIV PrEP

Variables: Individual data elements will be collected as available after enrollment and while participating in the registry. Data will include: age, gender at enrollment, weight and height, HIV risk factors, concurrent sexually transmitted infections, hepatitis B virus serostatus, hepatitis C virus serostatus, prior PrEP or post-exposure prophylaxis use, estimated glomerular filtration rate, serum phosphate, use of recreational drugs during sex, and PrEP adherence assessment. Pregnancy status will be requested for females. PrEP prescription/usage details will include: dose schedule, initiation (ie, prescription or self-initiation) date and stop date or duration of PrEP usage, and the tablet and refill quantity. If seroconversion occurs, additional data include date of seroconversion, circumstances of HIV acquisition if available, and results of HIV-1 resistance testing if available. Selected safety data for collection in the registry will include all fatal events, serious adverse drug reactions (SADRs), treatment-related renal or bone adverse drug reactions, and pregnancy reports. Possible factors leading to new HIV infection, genotypic resistance testing, and reason for PrEP discontinuation will also be collected.

Details on the participating institutions will include location and type of institution. HCP data will include provider specialty and if they routinely treat individuals with HIV-1 infection.

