9.4. Data Sources

This observational noninterventional registry will extract data from the individual's medical record. Data obtained from clinic visits, physical examinations, and medical records, including medical history, hepatitis history, prescribed medications, laboratory results, and safety data, will be captured while participating in the registry. HCPs will enter data into eCRF at each data collection point in a timely manner. If the HCP receives queries about data entered in the eCRF from the sponsor (or designee), the HCP will review the medical record and correct the eCRF data if necessary.

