9.6. Data Management

After finalization and approval of the protocol, an eCRF will be built in a commercial electronic data capture (EDC) system to collect the data listed in the variables section ([Table 9-1](#)). Personal identifying data such as names, health record identifiers, and national insurance numbers will not be collected.

HCP participants from each site will receive a unique username and password from the EDC system administrator following completion of the EDC system training. Completion of training and receipt of username/password will allow sites to enter data into the eCRF. HCPs will electronically sign the eCRF to confirm responsibility for the data following completion of data entry and data quality activities. Registry data will be stored on secure network drives with access restricted to authorized personnel only.

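### eGFR is collected without serum creatinine or the equation used, so values from different sites and age groups may not be comparable and cannot later be recalculated

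*Protocol*

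**What the plan says.** Three places in the protocol list the renal laboratory data, and they agree.

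- Section 9.3.4 (Laboratory Tests): "Renal function (estimated glomerular filtration rate [eGFR]), serum phosphate".
- The synopsis (Section 4, Variables): "estimated glomerular filtration rate, serum phosphate, use of recreational drugs during sex, and PrEP adherence assessment".
- Table 9-1 (Section 9.3.3): one row for eGFR and one for serum phosphate, each at baseline and each follow-up visit. There is no row for creatinine or for the eGFR equation.

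Section 9.3.4 describes the source: "Routinely collected laboratory values and date(s) of test(s) will be captured as available". No central laboratory or common calculation is mentioned. Section 9.6 ties the database to this list: "an eCRF will be built in a commercial electronic data capture (EDC) system to collect the data listed in the variables section", with a reference to Table 9-1.

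Most other inputs to an eGFR equation are collected. Table 9-1 has "Weight and Height" at baseline and follow-up, and age and gender at baseline, with transgender categories.

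On analysis, Section 9.7 says "Demographics and clinical characteristics of individuals on Truvada for PrEP will be analyzed" and that continuous variables will be summarised by mean, standard deviation, minimum, median and maximum. Results are shown overall and by subgroups that include adults and adolescents, gender and country. No eGFR summary is named.

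**The concern.** eGFR is not measured. It is computed from creatinine and patient characteristics, and the same blood sample gives different values under different equations. A registry that draws on routine records at many sites in five initial countries, and enrols both adults and adolescents, has no assurance that one equation lies behind all its values.

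The omission is at data capture, so it cannot be left to the statistical analysis plan. Without creatinine, eGFR cannot be recomputed. Without the equation, the reported values cannot be stratified or flagged. At stake is whether a descriptive mean or range of eGFR, overall or by subgroup, can be interpreted, and whether a difference between countries or age groups could be an artefact of the equation.

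**Working it through.** **1. Is the item really absent?** Creatinine and an eGFR equation appear in none of the synopsis variable list, Table 9-1 and Section 9.3.4. The general wording in Section 9.4, "including medical history, hepatitis history, prescribed medications, laboratory results, and safety data", names no further renal item, and the eCRF is built to Table 9-1. Section 9.3.4 does ask for the method of another test: "Virologic testing (HIV test methodology and results, hepatitis B serology, hepatitis C serology". Nothing equivalent is asked for eGFR.

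**2. Can eGFR be recomputed from what is collected?** Age, gender, weight and height are available. Creatinine is the missing measurement. Recorded gender also does not always settle the sex term, because Table 9-1 has transgender categories.

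**3. How far can the equation move a value?** The protocol gives no eGFR figure to reproduce. What follows is an illustration with assumed patients and the standard equations, neither of which comes from the documents. Creatinine (Scr) is in mg/dL.

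*Adult: male, 35 years, Scr 1.0.*
- MDRD: 175 × Scr^-1.154 × age^-0.203 = 175 × 1 × 0.486 = 85 mL/min/1.73 m2.
- CKD-EPI 2009, male, Scr above 0.9: 141 × (Scr/0.9)^-1.209 × 0.993^age = 141 × 0.880 × 0.782 = 97 mL/min/1.73 m2.
- Difference: 97 − 85 = 12 mL/min/1.73 m2.

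*Adolescent: male, 16 years, 168 cm, Scr 0.8.*
- Bedside Schwartz: 0.413 × height/Scr = 0.413 × 168/0.8 = 87 mL/min/1.73 m2.
- CKD-EPI 2009 (an adult equation), male, Scr below 0.9: 141 × (Scr/0.9)^-0.411 × 0.993^age = 141 × 1.050 × 0.894 = 132 mL/min/1.73 m2.
- Difference: 132 − 87 = 45 mL/min/1.73 m2. This arises only if an adult equation is applied to an adolescent.

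*Sex term: the same adult, CKD-EPI 2009 with the female term.*
- 141 × 1.018 × (1.0/0.7)^-1.209 × 0.993^35 = 141 × 1.018 × 0.650 × 0.782 = 73, against 97 with the male term.

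**4. What would that do to a summary?** If a share w of the values carries an equation offset d, the mean shifts by w × d and the variance rises by w(1 − w)d².
- With w = 0.5 and d = 12, the mean shifts by 0.5 × 12 = 6 and the added SD component is √(0.25 × 144) = 6.
- With d = 0 (one equation at all sites), both are zero.

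**5. Does the offset cancel within a person?** A constant offset does if the laboratory and equation stay the same. It need not here. Section 9.1 sets baseline at the start of Truvada and collects it retrospectively for people already on PrEP, including those who started before presenting to the participating HCP. Baseline and follow-up values may then come from different laboratories. An equation may also change when an adolescent becomes an adult.

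**The case against.** The strongest reply is that nothing the registry is committed to reporting depends on comparable eGFR values. That largely stands.

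- **Renal outcome.** Sections 9.3.2 and 9.7 name treatment-related renal reactions. Section 11.5 leaves causality to the investigator, and Section 11.4 brings in renal laboratory abnormalities through intervention, drug interruption, modification or discontinuation, or signs and symptoms. No eGFR threshold defines a case. A reader might infer that the renal safety outcome is compromised; the protocol does not support that.
- **Monitoring objective.** This needs to know whether and when eGFR was measured. Test dates are collected, and the equation is irrelevant to them.
- **Pooling on different scales.** A reader might also infer that eGFR values are in fact pooled on different scales. The protocol does not show that sites use different equations, and it names no eGFR summary or change from baseline. A summary follows only from the general rules for clinical characteristics and continuous variables. Results are also shown by country and by adults and adolescents, which limits mixing across those groups but not between sites within a country.
- **Size.** Cockcroft-Gault gives (140 − 35) × 75/(72 × 1.0) = 109 mL/min for the assumed adult at 75 kg, which suggests a gap of 109 − 85 = 24 from MDRD. That figure should not be used: Cockcroft-Gault is not indexed to 1.73 m2, so it mixes a unit difference with an equation difference.
- **Burden.** Section 9.9 makes reduced data collection a deliberate choice, and Section 7.2 explains why. The documents also do not say that creatinine is always in the record beside eGFR. Both are reasons to ask for the new fields only as available.

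What survives is narrow: the registry has chosen to collect eGFR at baseline and follow-up, and has left out what is needed to interpret it across sites.

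**Conclusion.** The point holds as a minor, inexpensive improvement to data capture. eGFR is collected without creatinine or the equation, so values from several countries, sites and two age groups may not be comparable and cannot be put on a common basis later. The main objectives and the investigator-judged renal reactions are not affected. The consequence is confined to any descriptive eGFR summary.

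The sizes of about 12 mL/min/1.73 m2 in an adult and up to about 45 in an adolescent rest on assumed patients. The second also needs an adult equation to have been applied to an adolescent. Nothing in the documents shows how often either occurs. The true effect could be zero, but the data as specified would not reveal which case applies.

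**What to change.** In Table 9-1 and Section 9.3.4, add as available:

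1. serum creatinine, with value, unit and date;
2. the equation behind the reported eGFR.

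Base eGFR summaries on values computed centrally, with one stated equation for adults and one for adolescents, and a stated rule for the sex term in transgender participants. Show site-reported eGFR separately where creatinine is unavailable, labelled with its equation if known. The synopsis variable list should be updated to match.

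The cost is slightly more data entry and one derivation. No extra test or visit is involved. The change is cheapest before the eCRF is built.
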